11.2 CLINICAL LABORATORY PARAMETERS

Descriptive statistics for clinical laboratory values and changes from baseline values at each assessment timepoint will be presented for the OLTP and by treatment group for the DBTP in International System of Units (SI units). There is a central lab transition (from Q2 to Covance) during the clinical trial. In addition, descriptive statistics for clinical laboratory values and changes from baseline values at each assessment timepoint will also be presented by central lab for the OLTP and by treatment group for the DBTP in SI units.

The descriptive statistics will be provided for the following laboratory parameters:

Hematology	Absolute and differential white blood cell count, erythrocyte count, hemoglobin, hematocrit, platelet count, and red blood cell indices (mean corpuscular volume, mean corpuscular hemoglobin, and mean corpuscular hemoglobin concentration)
Chemistry	Sodium, potassium, calcium, chloride, bicarbonate, glucose, blood urea nitrogen, creatinine, total protein, alkaline phosphatase, albumin, total bilirubin, direct bilirubin, indirect bilirubin, AST, ALT, Free T3, free T4, TSH, lactate dehydrogenase, creatine phosphokinase, γ -glutamyl transpeptidase, uric acid, phosphate, lipid panel (total cholesterol, triglycerides, low density lipoproteins, high density lipoproteins), prolactin, insulin, and magnesium
Urinalysis	Specific gravity, pH, protein, glucose,

Hemoglobin A_{1c}

In addition, descriptive statistics for values and changes from the baseline values in conventional units at each assessment time point will be presented for selected clinical laboratory parameters listed in [Appendix III](#). A description of reporting the lab values in conventional units in patient narratives (along with the standard reporting in SI units) is presented at the end of [Appendix III](#). Only patients with selected clinical laboratory data at baseline and at least one postbaseline visit during the OLTP and DBTP will be included in the summary.

Clinical laboratory test values will be considered potentially clinically significant (PCS) if they meet either the lower-limit or higher-limit PCS criteria listed in [Table 11-1](#). The number and percentage of patients who have PCS postbaseline clinical laboratory values will be tabulated overall for the OLTP, and by treatment group for the DBTP. The percentages will be calculated relative to the number of patients with available non-PCS baseline values and at least 1 postbaseline assessment for the corresponding periods (OLTP or DBTP). The numerator will be the total number of patients with available non-PCS baseline values and at least 1 PCS postbaseline value for the corresponding periods (OLTP or DBTP). A supportive tabular display of patients with PCS postbaseline values will be provided, including the PID number, study center number, and baseline and all postbaseline (including non-PCS) values.

In addition, a tabular display showing all AEs that occurred in patients who had PCS postbaseline clinical laboratory values will be provided.

Potential Hy's Law criteria within a 24-hour window is defined by a post baseline elevation of alanine aminotransferase (ALT) or aspartate aminotransferase (AST) $\geq 3x$ ULN, along with total bilirubin (TBL) $\geq 2x$ ULN and a non-elevated alkaline phosphatase (ALP) $< 2x$ ULN, all based on blood draws collected within a 24-hour period.

Patients who meet the potential Hy's Law criteria during the OLTP will be summarized for the OL Safety Population. Patients who meet the potential Hy's Law criteria from the first dose of DB IP to within 30 days after the last dose of DB IP will be summarized for the DB Safety Population. Supportive tabular displays will also be provided.

The number and percentage of patients with treatment-emergent significant changes in lipids parameters (total cholesterol, LDL cholesterol, HDL cholesterol, and triglycerides) and glucose will be tabulated by treatment group for the OLTP and the DBTP. The criteria for treatment-emergent significant changes in lipids and glucose are specified in [Table 11-2](#) and [Table 11-3](#). Percentages will be calculated relative to the number of patients with baseline values meeting the specified baseline criteria and with at least one postbaseline assessment during the specific period. The change in lipids and glucose from baseline to the highest (lowest for HDL cholesterol) postbaseline measurement during the specific period will be summarized. Supportive listings of patients with treatment-emergent changes in lipids and glucose values will be provided.

Table 11-1 Criteria for Potentially Clinically Significant Laboratory Tests

Laboratory Parameter	SI Units	Conversion Factor ^a	Traditional Units	PCS Criteria ^b Low Values	PCS Criteria ^b High Values
Hematology					
Hemoglobin	g/L	0.1	g/dL	< 0.9 × LLN	—
Hematocrit	volume fraction	100	%	< 0.9 × LLN	—
Eosinophils	%	1	%	—	> 10
Neutrophils	%	1	%	< 30	> 90
Basophils	%	1	%	—	> 6
Monocytes	%	1	%	—	> 20
Lymphocytes	%	1	%	< 10	> 60
Abs Neutrophils (ANC)	10 ⁹ /L	1	1000/µL	< 1.0	—
Platelet count	10 ⁹ /L	1	1000/µL	≤ 75	≥ 700
White blood cell count	10 ⁹ /L	1	1000/µL	≤ 2.5	≥ 15
Chemistry					
Albumin	g/L	0.1	g/dL	< 0.9 × LLN	> 1.1 × ULN
Alkaline phosphatase	U/L	1	U/L	—	≥ 3 × ULN
ALT	U/L	1	U/L	—	≥ 3 × ULN
AST	U/L	1	U/L	—	≥ 3 × ULN
GGT	U/L	1	U/L	—	≥ 3 × ULN
LDH	U/L	1	U/L	—	≥ 3 × ULN
Blood urea nitrogen	mmol/L	2.8011	mg/dL	—	> 1.2 × ULN
Calcium	mmol/L	4.008	mg/dL	< 0.9 × LLN	> 1.1 × ULN
Chloride	mmol/L	1	mg/dL	< 0.9 × LLN	> 1.1 × ULN
Cholesterol	mmol/L	38.6698	mg/dL	—	> 1.3 × ULN
HDL	mmol/L	39	mg/dL	< 0.8 × LLN	—
LDL	mmol/L	39	mg/dL	—	> 1.2 × ULN
CPK	U/L	1	U/L	—	> 1.5 × ULN
Creatinine	µmol/L	0.0113	mg/dL	—	> 1.3 × ULN
Glucose, fasting	mmol/L	18.018	mg/dL	< 0.8 × LLN	> 1.2 × ULN
Magnesium	mmol/L	2	mEq/L	< 0.9 × LLN	> 1.1 × ULN
Potassium	mmol/L	1	mEq/L	< 0.9 × LLN	> 1.1 × ULN
Sodium	mmol/L	1	mEq/L	< 0.9 × LLN	> 1.1 × ULN
Total bilirubin	µmol/L	0.0585	mg/dL	—	> 1.5 × ULN
Total protein	g/L	0.1	g/dL	< 0.9 × LLN	> 1.1 × ULN
Triglycerides, fasting	mmol/L	88.4956	mg/dL	—	> 1.2 × ULN
Uric acid	µmol/L	0.0168	mg/dL	—	> 1.1 × ULN
Urinalysis					
Protein	—	—	—	—	At least 2 +
Glucose	—	—	—	—	At least 2 +
Blood	—	—	—	—	At least 2 +

a Conversion factor from SI units to traditional units.

b Criteria refer to SI units.

ALT = alanine aminotransferase; AST = aspartate aminotransferase; CPK = creatine phosphokinase; GGT = gamma glutamyl transferase; HDL = high-density lipoprotein; LDH = lactate dehydrogenase; LDL = low-density lipoprotein; LLN = lower limit of normal laboratory reference range; PCS = potentially clinically significant; SI = *Le Système International d'Unités* (International System of Units); ULN = upper limit of normal laboratory reference range.

Table 11-2 Criteria for Treatment-emergent Significant Changes in Glucose

Criteria	Baseline	Postbaseline
Fasting Serum Glucose		
Normal to High	< 100 mg/dL	≥ 126 mg/dL
Impaired Fasting Glucose to High	100-125 mg/dL	≥ 126 mg/dL
Normal/Impaired Fasting Glucose to High	< 126 mg/dL	≥ 126 mg/dL
Change in fasting serum glucose ≥ 10 mg/dL at any time postbaseline	Any value	increase from baseline ≥ 10 mg/dL
Non-Fasting Serum Glucose		
Normal to High	< 140 mg/dL	≥ 200 mg/dL
Borderline to High	140-199 mg/dL	≥ 200 mg/dL
Normal to Borderline/High	< 140 mg/dL	≥ 140 mg/dL
Normal/Borderline to High	< 200 mg/dL	≥ 200 mg/dL
Change in non-fasting serum glucose ≥ 20 mg/dL at any time postbaseline	Any value	increase from baseline ≥ 20 mg/dL

Table 11-3 Criteria for Treatment-emergent Significant Changes in Lipids

Criteria	Baseline	Postbaseline
Total Cholesterol (Fasting and Non-Fasting)		
Normal to High	< 200 mg/dL	≥ 240 mg/dL
Borderline to High	≥ 200 and < 240 mg/dL	≥ 240 mg/dL
Normal/Borderline to High	< 240 mg/dL	≥ 240 mg/dL
Normal to Borderline/High	< 200 mg/dL	≥ 200 mg/dL
LDL Cholesterol (Fasting)		
Normal to High	< 100 mg/dL	≥ 160 mg/dL
Borderline to High	≥ 100 and < 160 mg/dL	≥ 160 mg/dL
Normal/Borderline to High	< 160 mg/dL	≥ 160 mg/dL
Normal to Borderline/High	< 100 mg/dL	≥ 100 mg/dL
HDL Cholesterol (Fasting and Non-Fasting)		
Normal to Low	≥ 40 mg/dL	< 40 mg/dL
Triglycerides (Fasting)		
Normal to High	< 150 mg/dL	≥ 200 mg/dL
Normal to Very High	< 150 mg/dL	≥ 500 mg/dL
Borderline to High	≥ 150 and < 200 mg/dL	≥ 200 mg/dL
Borderline to Very High	≥ 150 and < 200 mg/dL	≥ 500 mg/dL
Normal/Borderline to High	< 200 mg/dL	≥ 200 mg/dL
Normal/Borderline to Very High	< 200 mg/dL	≥ 500 mg/dL
Normal to Borderline/High/Very High	< 150 mg/dL	≥ 150 mg/dL
Treatment-emergent very high triglycerides (fasting)	Fasting triglycerides < 500 mg/dL	Fasting triglycerides ≥ 500 mg/dL

Table 11-3 Criteria for Treatment-emergent Significant Changes in Lipids

Criteria	Baseline	Postbaseline
Total Cholesterol (Fasting and Non-Fasting)		
Treatment-emergent very high triglycerides (non-fasting and random)	< 500 mg/dL	≥ 500 mg/dL
Treatment-emergent triglycerides > 1000 mg/dL (All cases—fasting, non-fasting, and random)	Triglycerides < 1000 mg/dL	Triglycerides ≥ 1000 mg/dL
Change in fasting or non-fasting total cholesterol ≥ 40 mg/dL at any time postbaseline	Any value	Increased ≥ 40 mg/dL
Change in fasting LDL cholesterol ≥ 30 mg/dL at any time postbaseline	Any value	Increased ≥ 30 mg/dL
Change in fasting or non-fasting HDL cholesterol ≥ 20 mg/dL at any time postbaseline	Any value	Decreased ≥ 20 mg/dL
Change in fasting triglycerides ≥ 50 mg/dL at any time postbaseline	Any value	Increased ≥ 50 mg/dL

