9. The patient experiences 1 of the following elevated liver enzyme conditions, which is confirmed by repeat testing within 48 to 72 hours of awareness:
 - ALT or AST $> 3 \times$ ULN and total bilirubin $> 2 \times$ ULN,
 - ALT or AST $> 8 \times$ ULN,
 - ALT or AST $> 5 \times$ ULN for more than 2 weeks,
 - ALT or AST $> 3 \times$ ULN with the appearance of jaundice, worsening of fatigue, nausea, vomiting, right upper quadrant pain or tenderness, fever, rash, or eosinophilia.
10. The patient has an absolute neutrophil count of < 1000 per mm^3 and, after repeat testing within 24 hours of awareness, the values are not normalized or are not increasing;
11. A female patient becomes pregnant during treatment.

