9.5 Potential Hy's Law Cases

Criteria for potential Hy's Law cases are as follows:

- ALT or AST $\geq 3 \times$ ULN AND
- Total bilirubin $\geq 2 \times$ ULN AND
- Alkaline phosphatase $< 2 \times$ ULN

Study site personnel must report every patient who meets these 3 criteria. Typically, all 3 analytes will be obtained from the same sample, but they may come from multiple samples taken within a 24-hour period. This requirement applies from the time the patient signs the ICF for the trial until 30 days after the final protocol-defined study visit or the last known dose of IP (if the final visit does not occur).

A laboratory alert for potential Hy's Law cases will be in place, and will notify investigators and the sponsor immediately when the above criteria have been met. A potential Hy's Law case must be faxed/mailed to the sponsor on the SAE/AESI form as soon as possible (within 24 hours of learning of the potential Hy's Law) to the following SAE/pregnancy fax number/email address, even if no AE has occurred:

[contact] (back-up [contact])

Email: [contact]

The eCRF pages for potential Hy's Law cases must be completed within 7 calendar days. Every effort to determine the cause of the liver enzyme abnormalities must be made, and close monitoring must be initiated in conjunction with the study physician and in accordance

with the FDA “Guidance for Industry: Drug-Induced Liver Injury-Pre-Marketing Clinical Evaluation” Jul 2009.

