6.7 DOUBLE-BLIND INTENT-TO-TREAT POPULATION

The DB ITT population will consist of all patients who took at least 1 dose of DB IP and had at least 1 post-randomization assessment of the PANSS or CGI-S scores during the DBTP of the study.

Patients will be included in the randomized treatment group for the DB ITT population.

7.0**STUDY PATIENTS****7.1****PATIENT DISPOSITION**

The OLTP starts with the first dose of OLTP and ends with one of the following: the last scheduled assessment at the Visit 13/end of OLTP (Week 18) or early termination (ET) before Visit 13 (Week 18) for patients who do not enter the DBTP; or 1 day before the first dose of DBTP (or the date of the first dose of the DB IP if the last scheduled assessment date in the OLTP is on the date of the first dose of the DBTP) for patients who enter the DBTP.

The DBTP starts with the first day of randomization and ends with the last scheduled assessment at Visit 26 (Week 44) or ET.

The SFU period starts one day after the end of the previous period and ends with the last available assessment. For patients without Visit 27 (Week 46) or Visit 28 (Week 48) assessment, the SFU period would not be derived.

Screen-failure patients (ie, patients screened but not included in the OL Safety Population) and the associated reasons for failure will be tabulated overall for the Screened Population.

The number and percentage of patients in the Screened, OL Safety and OL ITT Populations will be summarized overall and by study center. The number and percentage of patients in the Randomized, DB Safety, and DB ITT Populations will be summarized overall by treatment group and by treatment group and study center.

The number and percentage of patients in the OL Safety Population, who prematurely discontinued from the OLTP, who completed the OLTP, who entered the DBTP, and who entered the SFU period will be summarized overall and by reasons for premature discontinuation as recorded on the respective disposition pages of the electronic case report form (eCRF).

Similarly, the number and percentage of patients in the DB Safety Population who completed the DBTP, who prematurely discontinued from the DBTP, and who entered the SFU period will be summarized overall, by DB treatment group and by reasons for premature discontinuation as recorded on the respective disposition pages of the eCRF. Patients who relapse during the DBTP will also be summarized as completing the study.

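### SAP 11.2 counts potential Hy's Law cases to 30 days after the last dose in the DB Safety Population but only to the end of the OLTP in patients who are never randomised

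*SAP*

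**What the plan says.** SAP 11.2 (Clinical Laboratory Parameters) defines a potential Hy's Law case as ALT or AST at least 3 x ULN, total bilirubin at least 2 x ULN and alkaline phosphatase below 2 x ULN, "all based on blood draws collected within a 24-hour period". It then sets two counting windows in adjacent sentences:

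- Open-label: patients who meet the potential Hy's Law "criteria during the OLTP will be summarized for the OL Safety Population".
- Double-blind: cases are counted "from the first dose of DB IP to within 30 days after the last dose of DB IP", for the DB Safety Population.

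SAP 7.1 (Patient Disposition) fixes where the OLTP stops. For patients who are not randomised it ends at the last scheduled Visit 13 assessment, or at "early termination (ET) before Visit 13 (Week 18) for patients who do not enter the DBTP". After that, "The SFU period starts one day after the end of the previous period".

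Appendix IV, which selects the analyses for the abbreviated CSR, names one Hy's Law output: a patient listing whose label covers the OLTP and DBTP only.

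Protocol 9.5 has sites report every potential case from consent "until 30 days after the final protocol-defined study visit or the last known dose of IP", the second limit applying if the final visit does not take place. It makes no distinction between randomised and non-randomised patients.

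**The concern.** Both groups have taken cariprazine, and both stop it and enter a four-week follow-up. Only the group that reached randomisation has a Hy's Law window that extends past the last dose. The SAP gives no reason for the difference.

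Hepatic safety conclusions can turn on a single potential Hy's Law case. Under the present wording, the sponsor could receive a site report of such a case in an open-label patient shortly after ET while the Hy's Law output for that population shows none. The two populations would also be described with unequal follow-up, in a count that readers will tend to set side by side.

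**Working it through.** **1. How many patients the narrower window covers.** The inputs are in SAP 14.0: 345 to be randomised, 33.3% of open-label patients randomised, 1035 entering the OLTP.

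- Plan's own figure: 345 / (1/3) = 1035, as stated.
- Not randomised: 1035 - 345 = 690.
- Share: 690 / 1035 = 66.7%.

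These are planned numbers. SAP 4.0 records that the study was terminated early, and the documents do not give the actual share.

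**2. The windows side by side.**

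| Patient | Hy's Law counting in SAP 11.2 | After the treatment period |
|---|---|---|
| Randomised and dosed | OLTP, then first DB dose onward | To 30 days after last DB dose |
| Not randomised | OLTP only | None after ET or Visit 13 |

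For a randomised patient the OLTP runs up to the first DB dose, so cover is continuous. The gap exists only for those who leave before randomisation.

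**3. Which samples can fall in the gap.** Protocol Table 4 schedules chemistry at Visits 1, 8, 13, 18, 22 and 26/ET. Protocol 8.4.7 schedules none at Visits 27 and 28. The ET sample itself falls inside the OLTP and is counted. What remains is unscheduled or repeat testing, for which there are two routes:

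- Protocol 8.4.7 allows laboratory studies during the SFU at the investigator's discretion and uses that period to follow up abnormal findings.
- Protocol 8.9 item 9 refers to liver elevations "confirmed by repeat testing within 48 to 72 hours of awareness" when one of its four triggers is met.

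**4. What such a sample must show.** Because of the 24-hour rule, a repeat two or three days later cannot be combined with the ET sample. The later draw must meet all three limits itself. One case that fits both rules: the ET sample has ALT above 8 x ULN with bilirubin below 2 x ULN. This meets an item 9 trigger but not the Hy's Law definition. The repeat then has ALT at least 3 x ULN, bilirubin at least 2 x ULN and alkaline phosphatase below 2 x ULN. The site must report it under Protocol 9.5. In a non-randomised patient the repeat falls in the SFU period and SAP 11.2 does not count it. In a randomised patient within 30 days of the last DB dose, it does.

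**5. Whether another rule closes the gap.** SAP 16.3 uses all postbaseline assessments for PCS determinations and puts all assessments in the data listings, but does not mention Hy's Law. SAP 11.1 tabulates TEAEs in the OL SFU period, but Protocol 9.5 requires a report even where there is no AE, so AE tables are not a dependable substitute. Appendix IV refers back to the SAP sections for detail and adds no longer window. None of these classifies the patient as a potential Hy's Law case.

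**The case against.** The strongest reply is that little is lost in practice. Neither group has a scheduled liver test after ET, so the 30-day difference contains no planned sample. The raw values do not disappear: they are in the laboratory data listings. If ALT or AST was already at least 3 x ULN at ET with a non-PCS baseline, the patient is in the OLTP PCS table, and the supporting display shows all postbaseline values. The abbreviated CSR, moreover, has no Hy's Law summary table, only the listing. All of this stands, and it limits the point to how a few discretionary draws are classified.

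Four stronger readings are tempting, and the documents do not support them:

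- A reader might infer that such a case appears nowhere. It is absent only from the Hy's Law summary and listing.
- A reader might take 66.7% as the share of patients whose cases are missed. It is the planned share to whom the narrower window applies; the documents give no rate of post-ET draws or of cases.
- A reader might suppose that ALT at least 3 x ULN with bilirubin just under 2 x ULN at ET obliges a repeat under item 9. Without the listed symptoms or another trigger, it does not.
- A reader might argue that both windows must run to the end of the Protocol 9.5 reporting period, about 28 + 30 = 58 days after ET when Visit 28 takes place. Site reporting and statistical summary need not share an end date. Patients in the SFU are off IP and on usual treatment, and 30 days after the last dose is the limit Protocol 7.3.4.1 uses for AE summaries.

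None of this explains why the 30 days given to randomised patients is withheld from the rest.

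**Conclusion.** The inconsistency is real and narrow. For patients who do not enter the DBTP (690 of 1035 by plan, 66.7%), a qualifying draw after ET or Visit 13 is in no Hy's Law summary or listing, while SAP 11.2 counts the same draw in a randomised patient up to 30 days after the last dose. Only repeat or unscheduled draws that meet all three limits on their own are affected. The number of such cases is expected to be small and cannot be estimated from the documents.

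This rests on reading the OLTP in SAP 11.2 as defined in SAP 7.1, and on the Appendix IV listing following its label or the SAP 11.2 windows. The change is worth making because one case can matter and the correction is cheap. Alignment with the whole Protocol 9.5 reporting window is not required.

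**What to change.** - **SAP 11.2:** for patients who do not enter the DBTP, count potential Hy's Law cases from the first OL dose to within 30 days after the last OL dose, including repeat and unscheduled samples, to match the DB rule. Word it so that an ET sample counted today is not dropped if it falls later than that.
- **Appendix IV:** give the Hy's Law listing these same windows in place of the OLTP and DBTP label, for randomised and non-randomised patients alike.
- **Both outputs:** flag on-treatment and post-treatment cases separately.

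The cost is a short SAP edit, one changed date limit in programming and one flag. No new samples are needed and patient management does not change. The drawback is that a few post-treatment cases may reflect other medication started in the SFU; the separate flag lets the reader see which these are.

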11.3 VITAL SIGNS

Descriptive statistics (n, mean, SD, minimum, median, and maximum) for vital signs (supine systolic and diastolic blood pressures, supine pulse rate, weight, BMI, waist circumference, and temperature) and changes from baseline values at each visit and at the end of study will be presented overall for the OLTP and OL SFU period, and by treatment group for the DBTP and DB SFU period.

Vital sign values will be considered as PCS if they meet both the observed-value criteria and the change-from-baseline criteria listed in [Table 11-4](#). The number and percentage of patients with PCS postbaseline values will be tabulated overall for the OLTP, and by treatment group for the DBTP. The percentages will be calculated relative to the number of patients with available baseline values and at least 1 postbaseline assessment for the corresponding periods (OLTP or DBTP). The numerator will be the total number of patients with available baseline values and at least 1 PCS postbaseline value for the corresponding periods (OLTP or DBTP). A supportive tabular display of patients with PCS postbaseline values will be provided, including the PID number, study center number, and baseline and all postbaseline (including non-PCS) values.

In addition, a tabular display showing all AEs that occurred in patients who had PCS postbaseline vital sign values will be provided.

The number and percentage of patients with orthostatic hypotension will be provided for OLTP and DBTP. Orthostatic hypotension is defined as a reduction of ≥ 20 mm Hg in systolic blood pressure or a reduction of ≥ 10 mm Hg in diastolic blood pressure while changing from the supine to standing position. A supportive listing of patients with orthostatic hypotension will be provided. A listing of all AEs for patients with orthostatic hypotension will also be provided.

Table 11-4 Criteria for Potentially Clinically Significant Vital Signs

Parameter	Flag	Criteria^a	
		Observed Value	Change From Baseline
Supine systolic blood pressure, mm Hg	High	≥ 180	Increase of ≥ 20
	Low	≤ 90	Decrease of ≥ 20
Supine diastolic blood pressure, mm Hg	High	≥ 105	Increase of ≥ 15
	Low	≤ 50	Decrease of ≥ 15
Supine pulse rate, bpm	High	≥ 120	Increase of ≥ 15
	Low	≤ 50	Decrease of ≥ 15
Weight, kg	High	—	Increase of ≥ 7%
	Low	—	Decrease of ≥ 7%

a A postbaseline value is considered potentially clinically significant if it meets both the observed-value and the change-from-baseline criteria.

bpm = beats per minute.

As specified in the Seventh Report for the Joint National Committee on prevention, detection, evaluation and treatment of high blood pressure (NIH Publication No. 04-5230, 2004), hypertension status is defined in the following texts.

- Normotensive: systolic BP < 120 mm Hg and diastolic BP < 80 mm Hg.
- Prehypertension: systolic BP 120 to 139 mm Hg or diastolic BP 80 to 89 mm Hg
- Stage I Hypertension: systolic BP 140 to 159 mm Hg or diastolic BP 90 to 99 mm Hg
- Stage II Hypertension: systolic BP ≥ 160 mm Hg or diastolic BP ≥ 100 mm Hg

The number and percentage of patients with hypertension status changes from baseline will be provided for

- Shift of hypertension status from baseline to end of the OLTP in the OL Safety Population
- Shift of hypertension status from baseline to highest category during the OLTP in the OL Safety Population
- Shift of hypertension status from baseline to end of the DBTP in the DB Safety Population
- Shift of hypertension status from baseline to highest category during the DBTP in the DB Safety Population

Supportive listings of patients who have a shift in hypertension status from normotensive/prehypertension at Baseline to stage I/stage II hypertension will be provided.

